Blended Model of Integrated Care: In their roles as the National MH Director, Integrated Services, and National Primary Care Director for PC-MHI, [name] recently developed the Blended Model of integrated care, which includes clinical activities associated with both Care Management and Co-Located Collaborative Care. The Blended model was designed to be staffed by on-site PhD level psychologists, psychiatrists (or APN) and nurse care managers. Like the Co-Located Collaborative Care model, the psychologists and psychiatrists staff an open access clinic facilitated by warm handoffs from PCPs. All patients (regardless of diagnoses) referred to the co-located MHPs receive at least one telephone call from the care manager to follow-up with progress towards the treatment plan and the co-located MHPs can choose to involve the care manager for longer depending on the patient's need. PCPs can also choose to refer the patient (regardless of diagnosis) to the care manager directly, bypassing the co-located MHPs (e.g., to monitor antidepressant adherence). Thus, the Blended model addresses a wide array of disorders and behavioral problems commonly seen in PC settings. [name] have facilitated the implementation of the Blended Model at VAMCs nationwide. However, because there is no scientific evidence documenting that the Blended model is clinically effective in CBOCs lacking on-site psychiatrists and PhD psychologists, PC-MHI does not currently mandate that the Blended model be delivered in smaller CBOCs that serve rural Veterans.

Integrated Care for Veterans with Infectious Diseases: Hepatitis C Virus (HCV) afflicts approximately 5% or 1,100,000 Veterans³⁰; one quarter of HCV+ are also living with HIV.^{31,32} Comorbid mental health problems also disproportionately affect HCV+ and HIV+ individuals.^{33,34} Further, HCV, HIV, and their associated conditions (e.g., cirrhosis, depression, early mortality) are more prevalent among racial minority Veterans than white Veterans.³⁵ There are evidenced-based treatments for HIV, HCV, and comorbid depression, including Care Management; however, because of limited treatment rates, there appear to be several barriers to care that need to be explored and addressed in future interventions.

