Specific Aim 2 (Research Aim): Conduct a Hybrid Type 2 pragmatic effectiveness-implementation trial of the adapted Telemedicine Blended model by assessing **RE-AIM** outcomes including: provider **Reach** into the patient population, **Effectiveness** at improving clinical outcomes, **Adoption** by providers and **Implementation** fidelity.

Hypothesis 1 (Reach): Compared to Veterans who receive the Referral model, a higher proportion of Veterans who receive the Telemedicine Blended model will have a MH encounter over a 6 month period.

Hypothesis 2 (Effectiveness): Compared to Veterans who receive the Referral model, Veterans who receive the Telemedicine Blended model will have better clinical outcomes at the 6 month follow-up.

Specific Aim 3 (Exploratory Aim): In this exploratory study, we will conduct qualitative interviews to identify up to 40 Veterans' perception of factors associated with implementation of VA-approved treatments for HCV, HIV, and mental health treatment among Veterans with documented health disparities of HCV and HIV (i.e., racial minority Veterans). Specifically, we aim to:

- a. Identify Veterans' experiences and preferences for HCV and/or HIV and mental health treatment.
- b. Identify barriers and facilitators to accessing HCV and/or HIV and mental health treatment.

Because there is a lack of scientific evidence documenting that the Blended model is effective in smaller CBOCs, PC-MHI does not currently mandate that it be delivered in these facilities. If the proposed study is successful, our clinical partners, [name] (MHS), [name] (PC-MHI) will use the results to justify implementation of the Telemedicine Blended model. Further, we can harness information gained in our exploratory aim to begin developing implementation strategies to better treat racial minority Veterans with HCV and/or HIV and depression, possibly through Care Management.

Study Design:

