months prior to the first implementation period (for sites A and B) and continuing through the 6 month period following the implementation phase for sites E and F (see above diagram). We will exclude only those patients receiving specialty MH treatment in the 6 months prior to recruitment; those with a diagnosis of substance dependence; and those with a psychotic disorder diagnosis (schizophrenia, bipolar disorder, other psychotic disorders). Receipt of specialty MH care will be defined as having an encounter with a 500 series stopcode (except 534, which represents a PC-MHI encounter such as a telephone care manager encounter). The justification for this exclusion criterion is that patients enrolled in specialty MH care are already receiving a higher level of care than Telemedicine Blended and would not be expected to benefit clinically. The justification for excluding patients with substance dependence and a psychotic disorder diagnosis (schizophrenia, bipolar disorder, other psychotic disorders) is that currently there are no evidence based PC-MHI interventions for such patients. Finally, by focusing on all patients not already enrolled in specialty MH, it allows us to estimate the intervention's "population level impact" rather than its efficacy for a narrowly defined group of patients.⁵³

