Administrative Data: VA service utilization will be collected from the CDW, where all VA facilities upload and store encounter data, using methods we have employed previously.⁵⁴ Data will be collected on all patients at the study sites (hereafter referred to as the administrative sample) regardless of whether the patient was recruited and provided informed consent to participate in the primary data collection efforts associated with the trial. Encounter data will be collected for each patient for the 6 months following their first encounter in each 6-month observation period. Encounters to 500-599 stopcodes at CBOCs and VAMCs will be classified as MH. Encounters using the 534 stopcode (a stopcode used only for PC-MHI visits) will be classified as Telemedicine Blended. We will identify all patients (by scrambled social security number) with encounters to the study CBOCs and categorize them to the intervention or usual care group based on the date of their first encounter. We will also extract administrative data about MH diagnoses, age, gender, marital status, percent service connection and zipcode. MH diagnoses will be used to define diagnostic categories including: adjustment disorders, alcohol use disorders, anxiety disorders, attention deficit disorders, bipolar spectrum disorders, dementia, depressive disorders, drug use disorders, personality disorder, sleep disorders, stress reaction disorders, and other. The rurality of Veterans will be measured based on their zipcode using two different methods: 1) Rural Urban Commuting Area (RUCA) codes, and 2) VA definition. A zipcode to census tract crosswalk will be used. RUCAs are a census tract-based classification scheme that utilizes the standard Bureau of Census Urbanized Area and Urban Cluster definitions. RUCA also takes into account commuting patterns to Urbanized Areas, Urban Clusters, or smaller population centers to classify census tracts into 33 distinct categories, which typically are combined into 4 categories: 1) Urban - areas have Metropolitan cores and substantial commuting flow patterns to Urbanized Areas, 2) Large Rural Towns - have Micropolitan cores and substantial commuting patterns to Urban Clusters, 3) Small Rural Towns - have primary commuting flows to or within population centers of between 2,500 and 9,999 residents, and 4) Isolated Rural Towns - are less populated rural areas with no commuting flows to Urbanized Areas or Urban clusters.⁵⁵ VA's classification scheme defines census tracts that belong to Urbanized Areas as Urban and all others as Rural, except for those in counties with average population density of less than 7 residents per square mile, which are defined as Highly Rural.⁵⁵ The Real SSN Crosswalk file will be used to link primary data to the administrative data for participants enrolled in the effectiveness trial.

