
Dependent Variable for Adoption: Patients will be assigned to PCPs using the Patient Care Management Module from the Austin Automation Center which records every patient's PCP assignment start date and assignment end date. We have used this file successfully to measure provider adoption in a recent QUERI funded study (SDP 08-316). We will classify each Veteran in the administrative sample as having received Telemedicine Blended services if they had a 534 stopcode during their first encounter or a 534 stopcode encounter during the 6 month follow-up period. To measure provider adoption, we will categorize CBOC PCPs as adopters if they have at least one patient with the 534 stopcode encounter. In addition, we will document the percent of the PCP's patients that with a 534 stopcode encounter.

Data Analysis for Adoption - The percentage of PCPs adopting the intervention will be calculated. The adoption percentage will also be reported at the CBOC level.

Dependent Variable for Reach (Hypothesis 1): To measure Reach into the patient population, we will classify each Veteran in the administrative sample as having received MH services if they had a 500-599 series stopcode (including 534) during their first encounter or any encounter

during the 6 month follow-up period. Exploratory analysis will also examine *number* of MH encounters. We will also report the percentage of Veterans in the administrative sample who had a PC-MHI (534) stopcode during their first encounter or any encounter in the 6 month follow-up period in order to document the proportion randomized to the intervention who received Telemedicine Blended care.

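### The encounter that admits a Veteran to the Reach sample can also be the one that scores the Veteran as reached, so the intervention can alter the Hypothesis 1 denominator

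*Combined protocol and SAP*

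**What the plan says.** Hypothesis 1 is that, compared with Veterans under the Referral model, "a higher proportion of Veterans who receive the Telemedicine Blended model will have a MH encounter over a 6 month period".

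The sample is defined under Administrative Data. The plan takes all patients "with encounters to the study CBOCs and categorize them to the intervention or usual care group based on the date of their first encounter". It adds: "Encounter data will be collected for each patient for the 6 months following their first encounter in each 6-month observation period". No stopcode is required of, or excluded from, the first encounter.

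The outcome is defined under Dependent Variable for Reach (Hypothesis 1). Each Veteran is classified "as having received MH services if they had a 500-599 series stopcode (including 534) during their first encounter or any encounter" in the 6-month follow-up. The site rule for the outcome is wider than the rule for entry: "Encounters to 500-599 stopcodes at CBOCs and VAMCs will be classified as MH".

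On what the intervention adds, the Inclusion Criteria explain stopcode "534, which represents a PC-MHI encounter such as a telephone care manager encounter". The description of the Blended Model of Integrated Care says that patients referred to the co-located providers "receive at least one telephone call from the care manager". Purpose and Specific Aims describes proactive care-manager outreach between primary-care visits as the core of the Care Management component.

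**The concern.** A Reach denominator should be fixed without regard to whether the Veteran received the service. Here one encounter can satisfy both the entry rule and the success rule, and the intervention generates encounters of exactly that kind. If it brings into the sample Veterans who would otherwise have had no record in that period, they all arrive as successes. The Reach proportion could then rise with no change among Veterans who entered by another route.

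The analysis does not remove this. The casemix list under Data Analysis for Reach has no term for the type of entry encounter. Adjusting for MH diagnosis does not help, because the extra records are all reached within whatever diagnostic category they fall. The requirements for an upcoming primary-care appointment and no recent MH encounter, under Participant Recruitment and Consent, govern the interview sample and not the administrative sample.

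**Working it through.** The plan states no sample size, baseline rate or effect size for Hypothesis 1, so there is no figure of its own to reproduce.

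**1. How the route works.** Take a Veteran whose first encounter in period 1 is a primary-care visit with a referral in its last month, and who gets a care-manager call in the first month of period 2 and has no other clinic encounter in period 2.
- Planned rule, counted per period: the period 1 record is reached, because the call falls within 6 months. A period 2 record is also created, with the call as both index and success.
- Same Veteran without the call: no period 2 record.
- Primary-care index: the period 1 record is reached, and there is no period 2 record.

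**2. Conditions for an added record.** (a) The call falls in a later period than the primary-care visit. (b) The Veteran has no other encounter at the clinic in that period. (c) Veterans are counted once per period. (d) The call is recorded as an encounter at the study clinic. The text leaves (c) and (d) open.

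**3. Arithmetic.** Let p0 be the reached proportion among the other entrants, equal in both conditions (no true effect). Let f be the net extra 534-only entrants under the intervention, as a fraction of the other entrants. Each adds one to numerator and denominator:

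observed proportion = (p0 + f) / (1 + f); observed odds ratio = 1 + f / p0.

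For p0 = 0.20 and f = 0.02: 0.22 / 1.02 = 0.2157, or 21.6%; odds ratio 1 + 0.02 / 0.20 = 1.10.

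Both inputs are assumptions. Over a range:

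| p0 | f = 1% | f = 2% | f = 5% |
|---|---|---|---|
| 10% | 10.9% | 11.8% | 14.3% |
| 20% | 20.8% | 21.6% | 23.8% |
| 40% | 40.6% | 41.2% | 42.9% |

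The Background reports that 2.9% of primary-care encounters at CBOCs were PC-MHI encounters. That counts encounters, not Veterans, and predates this intervention, so it cannot supply f.

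**4. Offset.** If staff reallocation also removes MH-only entries equal to a fraction g, the observed proportion is (p0 + f - g) / (1 + f - g). With p0 = 0.20:
- f = 0.05, g = 0.02: 0.23 / 1.03 = 22.3%
- f = 0.05, g = 0.05: 0.20 / 1.00 = 20.0%
- f = 0.02, g = 0.05: 0.17 / 0.97 = 17.5%

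The sign therefore depends on f minus g, which the documents do not give.

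**The case against.** The strongest reply is that the route is narrow and its net direction unproven. Four parts of it stand.

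- All four conditions must hold together. Under (c), data are collected by period but group is set by the date of the first encounter, so once-only counting is a possible reading. In that case a call after an already sampled visit adds nothing. Under (d), the Adaptation section places the telephone care managers off site. A call logged at the parent VAMC would count as an outcome without creating entry.
- A reader might add open-access visits to the route. The Blended model description has these fed by warm handoffs from primary care, so most such Veterans already have a primary-care visit that day. Counting the first encounter is what captures those handoffs.
- A reader might infer that the rule can only add successes for the intervention. Usual-care Veterans also enter through MH visits at the clinic, and the Implementation section staffs the new model from existing MH providers. Only the difference between conditions biases the comparison.
- Hypothesis 1 speaks of Veterans, not of primary-care attenders, and someone called by a care manager has in fact been reached. Against a fixed panel the extra contacts are real reach. With f = 5% and attenders making up 70% or 90% of the panel, the panel gain is 0.05 × 0.70 = 3.5 or 0.05 × 0.90 = 4.5 points. The encounter-based rule shows 3.8 points from a 20% base, so it can overstate or understate the panel gain.

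These points limit size and direction. They do not answer the structural problem: entry can depend on the outcome and on the intervention. The plan's own framework section defines Reach over eligible or targeted patients. Its preliminary implementation study used a primary-care denominator (298 of 3,296 primary-care patients with depression not already in specialty care).

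**Conclusion.** The concern holds as a defect in how the Reach sample is defined. As written, an MH encounter may both admit a Veteran and score the Veteran as reached, in either condition, and the Blended model produces contacts that can do both. A bias toward the intervention is probable, because 534 outreach is what the model adds, but it is not certain. The claim that Hypothesis 1 is biased upward by a known amount goes beyond the documents, which give neither the base rate nor the number of 534-only entrants. The 21.6% reading from a 20% base assumes a 2% net excess, per-period counting and calls logged at the study clinic. If Veterans are counted once, or calls are logged at the parent VAMC, the effect shrinks or disappears. It is worth fixing because the remedy is cheap and removes the dependence on these unknowns.

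**What to change.** Under Administrative Data:
- Define the index as the Veteran's first primary-care (non-500-series) encounter at the study clinic in each observation period, and set group by that date.
- Count as reached any 500-599 encounter on that day or in the next 6 months. Same-day handoffs are kept.
- State whether a Veteran contributes once or once per period.
- Keep the all-encounter sample as a sensitivity analysis. Comparing the two shows how much the entry rule matters.

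The cost is one filter in the data extract and a few sentences in the plan. The downside is that Veterans seen only by MH in a period leave the main Reach analysis. Also, an MH contact before the first primary-care visit of a period counts only toward the preceding record, if it falls in that 6-month window. The index still depends on attendance after implementation. A panel drawn from the primary-care assignment file already named under Adoption would avoid that, but it answers a somewhat different question.

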Patient Recruitment: We will initiate recruitment at all sites 3 months into the first 6-month study period (labeled as “Identify Model” in the diagram above), during the implementation planning for Sites A and B. We will complete recruitment 3 months before the data analysis period begins. Thus, Veteran follow up will extend into the first 3 months of the data analysis period for all sites. Since the duration of the implementation period may vary from site to site, we will consider a site’s first referral to the Telemedicine Blended Model (with a PC-MHI telemedicine stopcode) as the index date with all Veterans enrolled prior to that date designated as controls and all Veterans enrolled after that date designated as intervention participants.

Figure 1: Implementation Timeline

Grant months	Identify Model	Intervention						Data Analysis
		6 months	6 months	6 months	6 months	6 months	6 months	
Site A	Implementation Planning	Implementation PDSA	Step Down					
Site B			Step Down					
Site C			Step Down					
Site D			Step Down					
Site E			Step Down					
Site F			Step Down					

Inclusion Criteria: We will sample from the patient population who screen positive on routinely administered VA MH screens (e.g., depression, alcohol, PTSD) at the 6 CBOCs, beginning 6

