CBOCs are the unit of randomization, with CBOCs randomized to an intervention start date using the stepped wedge design. A total of 6 CBOCs will participate in the study, with two CBOCs allocated to each of the 3 start dates. Randomization will be computer-generated by the statistician. A subset of potential patients (based on inclusion criteria) will be selected at each CBOC on a daily basis during the 5 measurement periods shown in Figure 1: Grant Activity Timeline (the formative evaluation control period(s), implementation, and step down period(s)).

Blinding

CBOCs and the research team will not be blinded to the intervention start dates. However, outcome assessment by independent evaluators (research assistants) will be blinded.

Statistical Analysis

The analyses will be conducted using the intention-to-treat principle, with CBOCs analyzed according to their randomized, crossover time irrespective of whether crossover took place at

the specified time. The results across the unexposed (control phase) observation periods will be compared with those across the observation periods in which the CBOCs are exposed to the Telemedicine Blended Model intervention (intervention phase). Characteristics of the patients and the CBOCs will be summarized by exposure status to examine potential selection bias or lack of balance.⁸¹ Because we have a small number (3) of randomization steps, we will compare numbers of patients analyzed, cluster (CBOC) size, CBOC characteristics and patient characteristics by randomization group. Patient-level data will be collected, with the primary analysis being patient-level.

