The CBOC-level analysis will examine the primary and secondary outcomes, summarized as the mean and standard deviation across CBOCs before and after implementation of Telemedicine Based care. At each facility, we will determine the index start date at which the first utilization of the telemedicine based service began. This will allow us to take into account the differing lengths of time it may take to implement the intervention at various CBOCs. Before this index date, patients participating in the study at that CBOC will be considered as being in the control period and those participating after the index date will be considered in the intervention phase. Analyses of before to after implementation will be conducted for continuous outcomes using linear mixed models. The interaction of intervention by CBOC will test if results differ by CBOC. We will adjust for baseline differences among CBOCs in the model.⁸²

The patient-level analysis will be a generalized linear mixed model (GLMM) which includes fixed terms for intervention (usual care referral model versus Telemedicine Based care) and time (6-month time periods for each step). The model will use random effects to model the correlation of patients within CBOCs.

The random effects model is:

$$Y_{ijl} = \mu + \beta_j + X_{ij}\theta + u_i + \varepsilon_{ijl} ; \\ u_i \sim N(0, \sigma^2_b) , \varepsilon_{ijl} \sim N(0, \sigma^2_w)$$

where β_j = fixed effect of time; $X_{ij} = 1$ if intervention, 0 otherwise; θ = intervention effect; u_i = random effect for cluster i ; ε_{ijl} = residual; $i = 1, 2, \dots, k$ clusters; $j = 1, 2, \dots, T$ time periods; and $l = 1, 2, \dots, m$ individuals.^{83, 84} In addition, we may consider adjusting the analyses to deal with lags in the intervention effect. This delayed intervention effect occurs if the intervention does not become fully effective during the step in which it is introduced.⁸⁵ If, for example, we expect the lag in the intervention effect to be 50% in the implementation step and 100% effective within 6 months, we could follow the suggestion of Hussey and Hughes of using fractional values for the treatment indicator.⁸³

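### Reach (Hypothesis 1) sorts patients by first-encounter date without naming the switch date; if that is the site's index date, infrequent attenders tend to become intervention and Reach is biased against the Blended model

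*Combined protocol and SAP*

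**What the plan says.** The Administrative Data section defines follow-up by period: "Encounter data will be collected for each patient for the 6 months following their first encounter in each 6-month observation period". It then says that patients will be identified and the study will "categorize them to the intervention or usual care group based on the date of their first encounter". No switch date is given for this sample.

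Under Dependent Variable for Reach (Hypothesis 1), a Veteran counts as reached "if they had a 500-599 series stopcode (including 534) during their first encounter or any encounter" in the 6-month follow-up.

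Two candidate switch dates appear elsewhere:

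- **Index date.** Patient Recruitment takes the site's first referral to the Telemedicine Blended Model "as the index date with all Veterans enrolled prior to that date designated as controls", and gives the reason: "Since the duration of the implementation period may vary from site to site". Statistical Analysis, under Hypothesis 2, repeats the idea: "At each facility, we will determine the index start date at which the first utilization of the telemedicine based service began".
- **Randomised step.** The same Statistical Analysis section promises intention-to-treat, with "CBOCs analyzed according to their randomized, crossover time". The Reach section itself describes its intervention denominator as those randomised to the intervention.

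Data Analysis for Reach lists a random intercept, treatment group, diagnostic categories, demographics, percent service connection and rurality. It has no attendance or prior-use covariate, no period term, and no rule for the period in which a site crosses over.

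**The concern.** The index date depends on when a site makes its first referral, and sites may first pilot for half a day a week for 2 months (Implementation section). It is therefore unlikely to coincide with a period boundary. When a boundary is crossed mid-period, first-encounter sorting is a selection on attendance: anyone seen before the index date is usual care, and only those not yet seen can become intervention. The outcome, any mental health encounter in 6 months, itself tends to rise with the number of visits. The two groups in that period would then differ on the outcome with no treatment effect at all. At stake is Hypothesis 1: a real gain in Reach would be understated, and a larger sample would not help.

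**Working it through.** The documents give no visit rate, Reach rate or power for Reach, so there is no plan figure to reproduce. From the plan come 6 CBOCs, two at each of 3 start dates, 5 measurement periods of 6 months, the sorting rule and the outcome definition. Visit rates, the link between visits and mental health use, and the point of crossover are assumptions. Successive pairs are taken to switch in periods 2, 3 and 4. Counted in pair-periods, that gives 6 wholly usual care, 3 split and 6 wholly intervention. All results are under no effect.

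**Sorting probabilities.** With visit rate λ per month and a switch c months into the period:

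- P(usual care) = 1 − exp(−λc)
- P(intervention) = exp(−λc) × [1 − exp(−λ(6 − c))]

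**Two-class example.** 20% attend monthly (λ = 1, 80% have mental health contact), 80% attend six-monthly (λ = 1/6, 10% have contact), and c = 3.

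- Monthly attenders: P(usual care) = 0.950, P(intervention) = 0.0473.
- Six-monthly attenders: 0.393 and 0.239.
- Usual-care Reach in the split period: (0.2 × 0.950 × 0.8 + 0.8 × 0.393 × 0.1) / (0.2 × 0.950 + 0.8 × 0.393) = 0.1835 / 0.5048 = 36.4%.
- Intervention Reach in the split period: (0.2 × 0.0473 × 0.8 + 0.8 × 0.239 × 0.1) / (0.2 × 0.0473 + 0.8 × 0.239) = 0.0267 / 0.2004 = 13.3%.
- Whole trial, logistic regression on expected counts with site and treatment: odds ratio 0.82. With period terms added: 0.55.

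**Gamma-Poisson example.** Visits per 6 months average 3, with gamma shape 1.5. Each visit is a mental health visit with probability 0.10, and the switch is at mid-period. Write L(s) = (1 + 2s)^−1.5. Reach for patients first seen between fractions a and b of the period is 1 − 0.9 × [L(0.1 + a) − L(0.1 + b)] / [L(a) − L(b)].

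- Whole period: 1 − 0.9 × 0.5860 / 0.8075 = 34.7%.
- Split period, usual care: 1 − 0.9 × 0.4543 / 0.6464 = 36.8% (36.7% by simulation). This group is 0.6464 / 0.8075 = 80% of patients seen.
- Split period, intervention: 1 − 0.9 × 0.1318 / 0.1611 = 26.4%.
- Mean visits per 6 months: 3.8 in usual care against 2.1 in intervention.
- Whole trial, usual care: (6 × 0.8075 × 0.347 + 3 × 0.6464 × 0.368) / (6 × 0.8075 + 3 × 0.6464) = 35.3%.
- Whole trial, intervention: (6 × 0.8075 × 0.347 + 3 × 0.1611 × 0.264) / (6 × 0.8075 + 3 × 0.1611) = 33.9%.
- Pooled odds ratio: (0.339 / 0.661) / (0.353 / 0.647) = 0.94.

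Simulating the same population with the switch at one quarter, one half and three quarters of the period gives odds ratios of 0.92, 0.94 and 0.97, or gaps of 1.9 to 0.7 points.

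**Range and controls.**

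- Over the gamma models tried, with differing dispersion, visit rates and crossover points, the whole-trial odds ratio is about 0.89 to 0.98 without period terms and about 0.71 to 0.93 with them. Stronger dispersion of attendance widens this a little.
- Equal visit rates for everyone: 1.00.
- Switch on a period boundary with one record per patient-period: 1.00.
- Split period dropped: 1.00.

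**The case against.** The strongest reply is that the premise is inferred. The index date is defined for enrolled Veterans and trial participants, not for the administrative sample. The study promises intention-to-treat analysis, and the Reach section speaks of those randomised to the intervention. If Reach follows the randomised step, this bias is absent. That stands: a reader might conclude that the plan definitely assigns Reach by the index date, and the documents do not say so. But with a switch on a period boundary, sorting by first-encounter date would add nothing to the period label, so the rule as worded invites the other reading.

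Three further inferences go beyond the documents:

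- **That the larger odds ratios describe the planned analysis.** They need period terms, which the Reach model does not list. They matter only if calendar time is added, as the Hypothesis 2 model does.
- **That the split-period contrast, 36% against 13%, is the trial result.** Split periods supply a minority of intervention records: 3 × 0.200 / (6 × 0.705 + 3 × 0.200) = 12% in the two-class case and 3 × 0.1611 / (6 × 0.8075 + 3 × 0.1611) = 9% in the gamma case. The sorting is a tendency, not a clean separation.
- **That each patient is classified once for the whole study.** This would be far worse (odds ratio about 0.40 in simulation). It is a strained reading, because the same section has just defined a first encounter within each observation period.

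Planned adjustment for diagnosis may help. In the two-class case a diagnosis flag with assumed 80% sensitivity and 90% specificity moves 0.82 to 0.87, and a near-perfect flag gives 1.00. In the gamma model the adjusted value was still 0.92. The bias also runs against the intervention, so it cannot by itself produce a false claim of benefit.

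**Conclusion.** The concern holds conditionally. The plan leaves the switch date for the Reach sample unnamed. Combined with the index date defined elsewhere, its sorting rule gives a biased Hypothesis 1 estimate under no effect. The direction requires only that the switch falls inside a period, that attendance varies between patients, and that mental health contact rises with attendance. The size rests on assumed visit rates. For the model as written, the null odds ratio is about 0.89 to 0.98 (roughly 1 to 2 points), and 0.82 in the two-class case. With period terms it is about 0.71 to 0.93, and 0.55. Whether this would hide or reverse a true gain cannot be judged, since the plan states no expected effect on Reach. In a sample of this kind it is not negligible. With 1,500 patients per site and records treated as independent, the log odds ratio has a standard error of about 0.024, so a null odds ratio of 0.936 lies near z = ln(0.936) / 0.024 ≈ −2.7. Repeat records per patient make that figure indicative only.

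**What to change.** In Administrative Data, replace sorting by first-encounter date with a stated rule:

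- **Primary, intention-to-treat.** Each 6-month CBOC-period belongs wholly to usual care or intervention according to the randomised step. Name the period in which each pair of sites begins to count as intervention. Every patient seen in a period takes that period's phase, with one record per patient-period.
- **Supportive, as-implemented.** Either exclude each site's split period, or restart equal 6-month periods at the index date and drop the short stub before it. The stub must go because a short window over-represents frequent attenders. In the two-class example they are 0.190 / 0.505 = 38% of patients seen in a 3-month stub, against 0.1995 / 0.705 = 28% in a full period.
- Apply the same rule to the reported uptake of stopcode 534.

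The cost is a short rewrite of the rule and a change to the extraction code, with no new data. The as-implemented analysis loses a small number of records. The intention-to-treat analysis accepts some dilution where a site crosses over late.
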